14.3 SAFETY DATA

14.3.1 EXTENT OF EXPOSURE

Table 14.3.1.1 Summary of Study Participation Duration – Safety Set (SS)

Table 14.3.1.2 Administration Modalities of IMPs – Safety Set (SS)

14.3.2 ADVERSE EVENTS

Table 14.3.2.1 Non-Treatment Emergent Adverse Events (NTEAEs) Occuring Before IMP Administration – Overview – Screened Patients Set (SPS)

Table 14.3.2.2 All NTEAEs by Primary System Organ Class and Preferred Term Occuring Before IMP Administration – Safety Set (SS)

Table 14.3.2.3 Treatment Emergent Adverse Events (TEAEs) occuring during the study period whatever the causal relationship – Overview – Safety Set (SS)

Table 14.3.2.4 All TEAEs by Primary System Organ Class and Preferred Term occurring during the study period whatever the causal relationship – Safety Set (SS)

Table 14.3.2.5 All TEAEs by Primary System Organ Class and Preferred Term occurring during the study period per causal relationship to IMPs and Study Procedure– Safety Set (SS)

Table 14.3.2.6 TEAEs requiring an AE-targeted medication by Primary System Organ Class and Preferred Term occurring during the study period whatever the causal relationship – Safety Set (SS)

CONFIDENTIAL	STATISTICAL ANALYSIS PLAN N° GDX-44-016 VERSION N° 4.0 (REF I011622)	F015830-03 Page 33 / 35
--------------	--	----------------------------

Table 14.3.2.7 TEAEs requiring an AE-targeted therapeutic measure by Primary System Organ Class and Preferred Term occurring during the study period whatever the causal relationship – Safety Set (SS)

Table 14.3.2.8 TEAEs requiring an AE-targeted procedure by Primary System Organ Class and Preferred Term occurring during the study period whatever the causal relationship – Safety Set (SS)

Table 14.3.2.9 TEAE requiring trial discontinuation by Primary System Organ Class and Preferred Term occurring during the study period whatever the causal relationship – Safety Set (SS)

Table 14.3.2.10 TEAE requiring IMP interruption by Primary System Organ Class and Preferred Term occurring during the study period whatever the causal relationship – Safety Set (SS)

Table 14.3.2.11 Serious TEAE by Primary System Organ Class and Preferred Term occurring during the study period whatever the causal relationship – Safety Set (SS)

Table 14.3.2.12. All Serious TEAEs by Primary System Organ Class and Preferred Term occurring during the study period per causal relationship to IMPs and Study procedure – Safety Set (SS)

Table 14.3.2.13 Serious TEAE leading to death by Primary System Organ Class and Preferred Term occurring during the study period whatever the causal relationship – Safety Set (SS)

Table 14.3.2.14 All AESI by Primary System Organ Class and Preferred Term occurring during the study period whatever the causal relationship – Safety Set (SS)

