The Mann-Whitney U-test will be used to test the difference in rCBV between the two trial arms by tumor grade categorization (high grade on one hand and low grade on the other hand) and between patients with high-grade and low-grade gliomas, within each of the two study arms at the significant level of 5%. The analysis will be performed for off-site readers.

Two analyses will be performed. The first one will consider the gliomas' grade categorization (high-grade versus low-grade) according to the stratification factor used at randomization, the second one will use the tumor grade categorization as per histological results (Standard of Truth) collected during the study.

Categorization as per histological results will be the following:

- Grade 1 and Grade 2 = Low grade,
- Grade 3 and Grade 4 = High grade.

The Benjamini-Hochberg method will be used to account for multiple testing.

Assessment and evaluation of the T2* signal intensity time curve (on-site and off-site assessment)

T2* signal intensity time curve will be visually assessed by on-site and off-site readers for the reliability of the curve in providing sufficient information for diagnosis purpose.

Number and percentage of patients for whom the reliability of the curve provides suffice information will be tabulated by trial arms.

For patients for whom the reliability of the curve provides suffice information, confidence in diagnosis will be presented for each arm using a 5-point scale:

- 1 = nil: very uncertain,
- 2 = poor: uncertain,
- 3 = moderate: moderately certain,
- 4 = high: good certainty,
- 5 = excellent: very certain.

Confidence in diagnosis will be summarized qualitatively and quantitatively by trial arm. The on-site and off-site read outcomes will be separately analyzed.

Assessment and evaluation of the T2* signal intensity time curve (off-site assessment)

Only for off-site readers, FWHM and the maximum signal drop will be compared between the trial arms using a Mann-Whitney U-test.

11.3.7 *Adverse Event*

All AEs will be coded using the MedDRA in force at the time of the data base lock.

An overall summary of AEs will be presented using the Screened Patient Set (SPS) to catch AEs of patients who did not receive trial drug that is to say Non-Treatment Emergent AEs (NTEAE). The table will be presented overall with the following variables:

- Total number of AEs.
- Total number of patients with at least one AE.

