2.3.2. Adverse Events

AEs will be recorded throughout patient's participation. AEs will be coded using the last version of MedDRA dictionary at the time of the database lock.

A Serious Adverse Event (SAE) is any untoward medical occurrence that at any dose (ICH E2A):

CONFIDENTIAL	STATISTICAL ANALYSIS PLAN N° GDX-44-016 VERSION N° 4.0 (REF I011622)	F015830-03 Page 11 / 35
--------------	--	----------------------------

- Results in death,
- Is life-threatening,
- Requires in patient hospitalization or prolongation of existing hospitalization,
- Results in persistent or significant disability / incapacity,
- Is a congenital anomaly / birth defect,
- Is an important medical event.

An Adverse Event of Special Interest (AESI) for this protocol is defined by suspected or confirmed Nephrogenic Systemic Fibrosis (NSF). The MedDRA code 10067467 corresponding to the PT “Nephrogenic systemic fibrosis” will be used to identify this AESI.

AEs emergence will be defined as follows:

- Non-treatment emergent AE (NTEAE): if the AE starts prior to the IMP administration or if the patient is not injected.
- Treatment emergent AE (TEAE): if the AE starts on the date and time or after the IMP administration.

TEAEs with causal relationship to the IMP are those described by the investigator with causal relationship to the IMP equals to “related” or missing relationship.

If an AE start date is missing or unknown, the AE will be considered as treatment emergent.

When the start date of an AE is only partially known, it will be categorized as not emergent or emergent using the following rules:

- If the partial start date is before ($<$) the IMP administration (i.e., year or year & month is/are before those of the date of the injection) then the AE is not emergent.
- If the partial start date is after (\geq) the IMP administration (i.e., year or year & month is/are the same as or after those of the date injection) then the AE is emergent.

Time to onset of AE will be calculated as follow: datetime of AE onset – datetime of IMP administration. If the AE start date is missing or unknown, it will be imputed as the treatment administration date.

When the start date of an AE is only partially known, it will be imputed so that the time to onset is minimal.

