5.2. Data Sets Analysed and protocol deviations

Data sets analysed

The patient sets for this trial, will be presented by arm and overall, and are defined below:

- Screened Patients Set (SPS) will include all patients having signed the ICF,
- All Randomized Patients Set (ARPS) will include all patients having signed the inform consent form and randomized according to the assigned treatment arm,
- All Randomized and Treated Patients Set (ARTPS) will include all patients having signed the inform consent form, randomized according to the assigned treatment arm and treated in the trial,
- Full Analysis Set (FAS) will include all patients who have a valid primary criterion assessment, that is to say images available, with a perfusion CBV map considered as technically adequate (i.e., poor fair, good) and read. Patients will be analysed according to the treatment arm assigned at randomization. Two FAS will be considered in this study:
 - Off-site FAS taking into account off-site assessments for the two off-site readers,
 - On-site FAS: taking into account on-site assessments.
- Per-Protocol Set (PPS) will include all patients from the FAS who have no major protocol deviations and who have complied with the treatment allocated at randomization. Two PPS will be considered in this study:
 - Off-site PPS: all patients from the Off-site FAS and without major protocol deviations for both assessments and specific to the off-site assessment,
 - On-site PPS: all patients from the On-site FAS and without major protocol deviations for both assessments and specific to the on-site assessment,
- Safety Set (SS) will include all patients having received at least one injection of IMP regardless of the quantity. Patients will be analysed according to the treatment really received.

CONFIDENTIAL	STATISTICAL ANALYSIS PLAN N° GDX-44-016 VERSION N° 4.0 (REF I011622)	DATED: DECEMBER 20, 2024	F015830-03 Page 17 / 35
--------------	--	--------------------------	----------------------------

Table 2: Datasets analysed

	Screened Patient Set (SPS)	Safety Set (SS)	Full Analysis Set (FAS)		Per Protocol Set (PPS)	
			Off-site FAS	On-site FAS	Off-site PPS	On-site PPS
Disposition	✓					
Protocol Deviation	✓					
Population characteristics at baseline			✓		✓	
Exposure		✓				
Efficacy: Primary criterion			✓		✓	
Efficacy: Secondary criteria			✓	✓	✓	✓
Safety		✓				
Data Listings	✓					

Protocol deviations

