5.6.2. Adverse Events

NTEAEs

An overall summary of NTEAEs will be presented using the SPS. The table will be presented with the overall "Total" column only.

CONFIDENTIAL	STATISTICAL ANALYSIS PLAN N° GDX-44-016 VERSION N° 4.0 (REF I011622)	F015830-03 Page 27 / 35
--------------	--	----------------------------

The total number of events and number of patients with at least one event will be tabulated for the following events:

- All NTEAEs,
- NTEAEs according to intensity (patients with AEs having different intensities will be counted in each category of intensity),
- NTEAEs according to the outcome (patients with AEs having different outcomes will be counted in each category of outcome),
- NTEAEs requiring an AE-targeted medication,
- NTEAEs requiring another AE-targeted action,
- NTEAEs leading to study discontinuation,
- Serious NTEAEs (variable “serious” classified as yes or missing) and by seriousness criteria (patients with AEs having different seriousness criteria will be counted in each category of seriousness criterion),
- AEs of special interest (AESIs) (preferred term is Nephrogenic systemic fibrosis).
- AEs with causal relationship to a study procedure.

Furthermore, the distribution of the number of AEs reported by patient (0, 1, 2 or 3 or more AEs) will be also presented.

The number and percentage of patients with at least one NTEAE and the number of NTEAE will be presented overall according to Primary SOC and PT.

TEAEs

The same overview will be displayed by arm for Treatment Emergent AEs (TEAEs) using the SS. The terms “NTEAE” will be replaced by “TEAE”. The following variables will be presented in addition:

- TEAEs with causal relationship to the IMP.
- TEAEs leading to interruption of the IMP.

The number and percentage of patients with at least one TEAE and the number of TEAE will be presented by arm and overall according to Primary SOC and PT.

TEAEs with Causal Relationship to the IMP

The number and percentage of patients with at least one TEAE with causal relationship to the IMP and the number of corresponding TEAE will be presented by arm and overall according to Primary SOC and PT. AEs with causal relationship to the IMP are those described by the investigator with causal relationship to the IMP “related” or missing.

TEAEs with Causal Relationship to a Study Procedure

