14.3.3 DEATHS, SERIOUS ADVERSE EVENTS AND OTHER SIGNIFICANT ADVERSE EVENTS

Table 14.3.3.1 Listing of Deaths - Safety Set (SS)

Table 14.3.3.2 Listing of Serious Adverse Events (other than Deaths) and AESI - Safety Set (SS)

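### The SOC/PT table of non-treatment-emergent AEs, and the death and SAE/AESI listings, use the injected-only Safety Set, so they omit patients who consented but were never injected

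*SAP*

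**What the plan says.** **Analysis sets (SAP 5.2).** "Screened Patients Set (SPS) will include all patients having signed the ICF". "Safety Set (SS) will include all patients having received at least one injection of IMP regardless of the quantity".

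**Definition (SAP 2.3.2).** An AE is an NTEAE "if the AE starts prior to the IMP administration or if the patient is not injected".

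**Purpose (Protocol 11.3.7).** The overall AE summary uses the SPS "to catch AEs of patients who did not receive trial drug that is to say Non-Treatment Emergent AEs (NTEAE").

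**Analysis text (SAP 5.6.2).** The NTEAE part opens: "An overall summary of NTEAEs will be presented using the SPS". It gives that overview a total column only. It then asks for NTEAEs by primary SOC and PT, presented overall, and names no set for that table. The Safety Set is first named in the next part, on TEAEs. For deaths, SAEs and AESIs the section says only that they will be listed, and gives sort keys.

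**Output list (SAP 6.1).** The title of Table 14.3.2.1 ends "Occuring Before IMP Administration – Overview – Screened Patients Set (SPS"). Table 14.3.2.2 is "All NTEAEs by Primary System Organ Class and Preferred Term Occuring Before IMP Administration – Safety Set (SS"). Output 14.3.3.1 is "Listing of Deaths - Safety Set (SS"), and 14.3.3.2, for other SAEs and AESIs, has the same set.

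**SAP Table 2.** The safety row is ticked for the Safety Set only. The data-listings row is ticked for the SPS.

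**The concern.** A patient can consent, have an event during screening and never be injected, sometimes because of that event. Protocol 10.4 lists an AE among the reasons for screen failure and discontinuation. The SPS was chosen for the AE overview so that such patients are counted. If the table that names the events is restricted to injected patients, the overview can show an NTEAE that its own breakdown cannot explain. If the death and SAE/AESI listings carry the same restriction, a death or serious event after consent, including one attributed to a trial procedure, is missing from the section of the report where a reader looks for it first.

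**Working it through.** No arithmetic on power, error rates or effect size applies. The check compares set definitions with output labels.

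**1. Who is in which set.** The SPS is every patient who signed the consent form. The Safety Set is every patient with at least one injection (SAP 5.2). A consented, non-injected patient is in the SPS and not in the Safety Set.

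**2. How that patient's events are classed.** Under the second limb of SAP 2.3.2, all AEs of a non-injected patient are NTEAEs. None can be a TEAE.

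**3. What the two NTEAE tables will show.** Let *a* be the number of NTEAEs in injected patients and *b* the number in non-injected patients.

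| Output | Set | NTEAEs included |
|---|---|---|
| Table 14.3.2.1, overview | SPS | *a* + *b* |
| Table 14.3.2.2, SOC/PT | Safety Set | *a* |

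The gap is (*a* + *b*) − *a* = *b*, exactly the events of non-injected patients. The tables reconcile on events only if *b* = 0. The percentages also have different denominators: all consented patients in one table, injected patients in the other.

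**4. The titles.** Both titles limit the table to events before IMP administration. For a patient with no administration that wording has no reference point. It reflects only the first limb of SAP 2.3.2, so read literally it could exclude non-injected patients even from the SPS overview.

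**5. The listings.** The same set logic applies: a non-injected patient cannot appear in 14.3.3.1 or 14.3.3.2. SAP 5.6.2 does not restrict these listings to injected patients, but it does not assign them to the SPS either. Table 2 can be read both ways, since they are safety outputs (Safety Set) and also listings (SPS). Every listing in SAP section 6.2 is on the SPS, and these two are the only listings in the SAP on the Safety Set.

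**6. Whether such events can exist in the data.** They can.
- Protocol 7.2.3 records AEs from signature of the consent form.
- Protocol 9.1.2, Table 3, collects unrelated SAEs, AESIs and related AEs at screening.
- Protocol 3.3.1 allows up to 7 days of screening.
- Protocol 14.3.2 requires AE data for screen failures.

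**7. What the report still holds.** Table 14.3.2.1 counts these events by intensity, outcome, seriousness criterion, study discontinuation, AESI status and relationship to a study procedure (SAP 5.6.2). Listing 16.2.7.2 lists every NTEAE on the SPS.

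**8. Size.** The documents give no expected number of non-injected patients and no pre-injection event rate, so *b* cannot be estimated. The difference between 138 enrolled and 124 evaluable patients (138 − 124 = 14) is an allowance for drop-out from the evaluable set, not a forecast of patients without an injection.

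**The case against.** The strongest reply has four parts.

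- **The SPS commitment is narrow.** Protocol 11.3.7 and SAP 5.6.2 tie the SPS to the overall summary, and Table 14.3.2.1 meets that. The protocol promises no SOC/PT table of NTEAEs. In SAP 5.6.2 the SPS and the total column belong to the overview sentence, and the SOC/PT sentence says only that results are presented overall. Table 14.3.2.2 can claim the safety row of Table 2. This stands as far as it goes: a reader might infer that SAP 5.6.2 prescribes the SPS for the SOC/PT table, and it does not say so. But the same safety row also conflicts with Table 14.3.2.1, so it cannot settle the matter, and two tables of the same events on different sets remain inconsistent.
- **The listings fit their text.** SAP 5.6.2 sorts them by actual arm and by date and time of IMP administration, which presumes an injection. This stands against calling the Safety Set label a breach. It does not prevent inclusion, because those fields can be left blank.
- **The events are reported elsewhere.** This stands in full. A reader might infer that deaths and SAEs of non-injected patients disappear from the report, but the SPS overview and Listing 16.2.7.2 rule that out.
- **Few events are likely.** Screening is at most 7 days and may fall on the MRI day, and a footnote to Protocol Table 3 lets non-serious, unrelated events before injection be recorded as medical history. This is fair and limits the weight of the point, but the footnote does not cover serious or procedure-related events.

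**Conclusion.** The point holds as a minor reporting correction. For Table 14.3.2.2 there is a clear inconsistency: it breaks down an SPS overview on a set that excludes, by definition, one of the two groups the NTEAE definition covers. For Listings 14.3.3.1 and 14.3.3.2 there is a completeness gap, resting on the collection of AEs and SAEs from consent and on the data-listings row of SAP Table 2.

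What non-injected patients lose is the SOC/PT summary of their events and a place in the dedicated death and SAE/AESI listings. The number affected is unknown and may be zero, in which case the event counts agree and only the denominators may differ. TEAE outputs are correctly on the Safety Set. Nothing here touches the arm comparison or the primary endpoint. The conclusion assumes that the outputs are programmed with the sets named in section 6.1.

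**What to change.** 1. Set Table 14.3.2.2 on the SPS, presented overall.
2. Remove the restriction to the period before IMP administration from the titles of both Table 14.3.2.1 and Table 14.3.2.2, so that both limbs of the SAP 2.3.2 definition are covered.
3. Set Listings 14.3.3.1 and 14.3.3.2 on the SPS with an injected/not-injected flag. Leave arm and IMP time blank for patients who were not injected.
4. In SAP 5.6.2, name the set for the NTEAE SOC/PT table and for the death and SAE/AESI listings.
5. In SAP Table 2, add to the safety row the exception that NTEAEs are presented on the SPS.

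The cost is three population labels, two titles, one flag, a sentence or two in SAP 5.6.2 and one entry in Table 2. No new data are needed, because AEs of screen failures are already collected.

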14.3.3 DEATHS, SERIOUS ADVERSE EVENTS AND OTHER SIGNIFICANT ADVERSE EVENTS

Table 14.3.3.1 Listing of Deaths - Safety Set (SS)

Table 14.3.3.2 Listing of Serious Adverse Events (other than Deaths) and AESI - Safety Set (SS)

14.3.4 CLINICAL LABORATORY DATA

14.3.5 VITAL SIGNS, PHYSICAL FINDINGS AND OTHER OBSERVATIONS RELATED TO SAFETY

14.3.6 CONCOMITANT MEDICATIONS AND PROCEDURES

Table 14.3.6.1 Concomitant Medications According to ATC Classification System –Safety Set (SS)

Table 14.3.6.2 Concomitant Procedures By Primary System Organ Class and Preferred Term – Safety Set (SS)

6.2. Contents of clinical study report section 16.2

16.2 PATIENT DATA LISTING

16.2.1 DISCONTINUED PATIENTS

Listing 16.2.1.1 Patient Disposition – Screened Patient Set (SPS)

Listing 16.2.1.2 Visit Dates – Screened Patient Set (SPS)

Listing 16.2.1.3 End Of Study – Screened Patient Set (SPS)

Listing 16.2.1.4 Inclusion Criteria Not Met at Screening (V1) and MRI / Randomisation Visit (V2) – Screened Patient Set (SPS)

Listing 16.2.1.5 Non-Inclusion Criteria Met at Screening (V1) and MRI / Randomisation Visit (V2) – Screened Patient Set (SPS)

16.2.2 PROTOCOL DEVIATIONS

Listing 16.2.2.1 Protocol Deviations – Screened Patient Set (SPS)

16.2.3 PATIENTS EXCLUDED FROM EFFICACY ANALYSIS

Listing 16.2.3.1 Analysis Data Sets – Screened Patient Set (SPS)

16.2.4 DEMOGRAPHICS AND BASELINE CHARACTERISTICS

Listing 16.2.4.1 Demographics At V1 and Weight At V2 – Screened Patient Set (SPS)

Listing 16.2.4.2 Patient Imaging History – Screened Patient Set (SPS)

CONFIDENTIAL	STATISTICAL ANALYSIS PLAN N° GDX-44-016 VERSION N° 4.0 (REF I011622)	F015830-03 Page 34 / 35
--------------	--	----------------------------

- Listing 16.2.4.3 Study Disease Diagnostic: Glioma – Screened Patient Set (SPS)
- Listing 16.2.4.4 Medical History – Screened Patient Set (SPS)
- Listing 16.2.4.5 Previous And Concomitant Medications – Screened Patient Set (SPS)
- Listing 16.2.4.6 Previous And Concomitant Procedures, Therapeutic Measures – Screened Patient Set (SPS)
- Listing 16.2.4.7 MRI examination – Screened Patient Set (SPS)
- Listing 16.2.4.8 Pregnancy Test – Screened Patient Set (SPS)

16.2.5 COMPLIANCE AND/OR DRUG CONCENTRATION DATA (IF AVAILABLE)

- Listing 16.2.5.1 Compliance Of IMPs – Screened Patient Set (SPS)

16.2.6 INDIVIDUAL EFFICACY RESPONSE DATA

- Listing 16.2.6.1 Technical adequacy of perfusion CBV map by off-site readers – Screened Patient Set (SPS)
- Listing 16.2.6.2 Diagnostic quality of CBV map generated by off-site readers – Screened Patient Set (SPS)
- Listing 16.2.6.3 Technical adequacy of perfusion CBV map and diagnostic quality of CBV map generated by on-site readers – Screened Patient Set (SPS)
- Listing 16.2.6.4 rCBV values by off-site readers – Screened Patient Set (SPS)
- Listing 16.2.6.5 Reliability of the T2* signal intensity time curve in providing sufficient information for diagnosis purpose by off-site readers – Screened Patient Set (SPS)
- Listing 16.2.6.6 Level of diagnosis confidence by off-site readers – Screened Patient Set (SPS)
- Listing 16.2.6.7 Reliability of the T2* signal intensity time curve in providing sufficient information for diagnosis purpose and Level of diagnosis confidence by on-site readers – Screened Patient Set (SPS)
- Listing 16.2.6.8 Full-Width at Half Maximum by off-site readers – Screened Patient Set (SPS)
- Listing 16.2.6.9 Maximal Drop by off-site readers – Screened Patient Set (SPS)
- Listing 16.2.6.10 Histopathology – Screened Patient Set (SPS)

